1.1 Background Information

Traumatic brain injury (TBI) is a leading cause of acquired disability in childhood, impacting long-term health and functioning. Hospitalizations and rehabilitation visits leave families with worries, guilt, and questions regarding longer-term issues. The impact of pediatric TBI on caregivers and families is clearly documented, with numerous studies showing poorer psychological functioning, greater stress, and more family problems among caregivers of children with TBI relative to caregivers of non-injured children (e.g., Aitken et al., 2009; Hawley et al., 2003; Rashid et al., 2014). Mounting evidence has supported the critical role of parent/family functioning and parent-child interactions in child recovery following TBI (Yeates et al., 1997; Taylor et al., 2001, Gerring & Wade, 2012), and recent investigations have continued to underscore the role of the family and home environment in the child's recovery.

Risk factors for poorer recovery include nonmodifiable factors such as greater severity of injury (Catroppa et al., 2008; Rassovsky et al., 2015), younger age at injury (Catroppa et al., 2008; Keenan et al., 2019), and lower household income (Cohen-Zimerman et al., 2019). However, there is a growing body of research documenting the critical role of caregiver and family functioning on child recovery following pediatric TBI (e.g., Ryan et al., 2016). Poor caregiver psychological functioning and family dysfunction have been found to exacerbate child behavior problems following injury (e.g., Raj et al., 2014a; Taylor et al., 2001). This association is particularly notable given that parents of children with TBI report more family problems, higher rates of depression and anxiety, and greater levels of stress than parents of non-injured children (e.g., Aitken et al., 2009; Hawley et al., 2003; Rashid et al., 2014). The influence of caregiver functioning is apparent in the initial months post injury, with poorer caregiver psychological health predicting more adolescent externalizing behavior problems, and more positive parent-adolescent communication predicting fewer behavior problems (Raj et al., 2014a).

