3.3 Study Measures

Participants will complete the following self-report measures at baseline, one-month post-baseline, and six-month follow-up. The measures described below were chosen based on the following criteria: 1) brevity (to minimize respondent burden), 2) high levels of reliability and evidence of validity with this population, 3) sensitivity to the effects of TBI, and 4) sensitivity to the effects of intervention. All data will be collected online via REDCap.

Family demographics: Parents will complete a demographic survey that includes items related to annual family income, child and parent race/ethnicity, relationship to child, and services child is receiving.

Parent mental health functioning: The Patient-Reported Outcomes Measurement Information System (PROMIS) Anxiety Measure 4a (4 items) will be used to assess parent anxiety. The Center for Epidemiological Studies Depression Scale (CES-D; 10-items), will be used to measure parent depression. The CESD-10 is the short form of the original 20 item CES-D (Radloff, 1977). The Primary Care PTSD Screen for DSM-5 (PC-PTSD-5) will be used to assess for parent post-traumatic stress symptoms. The measure consists of 5-items (Prins, et al., 2015).

Parent wellbeing: Parent resilience will be assessed using the Connor-Davidson

Resilience Scale (10 items, Connor and Davidson, 2003) and parent self compassion and self-care behaviors will be assessed using the Mindful Self-Care Scale – Brief (24 items, Cook-Cottone, C. P. (2015)

Perceived parenting efficacy. The Caregiver Self-Efficacy Scale (CSES) is a 25 item self-report scale that measures parenting confidence and efficacy. Parents rate how comfortable they are in aspects of parenting, including their ability to control their child's behavior, praise their child, and say no to their child. Scores on the measure range from 25 to 100, with higher scores indicating greater perceived parenting efficacy. The CSES is a reliable and valid measure and has been shown to be sensitive to the effects of online, family-centered interventions for TBI (Wade et al., 2014).

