3.5 Recruitment Procedures

Up to 200 participants will be enrolled in this RCT. Potential participants will be identified and recruited from the CCHMC and NCH Trauma Registry, inpatient units, and outpatient clinics such as rehabilitation clinics. Potential participants will also be recruited through sharing of study information and study flyer at other hospitals and through organizations and associations serving children/families impacted by pediatric TBI.

Recruitment at CCHMC and NCH

Parents/caregivers who are eligible to participate will receive the study brochure or flyer while they are at the hospital, when their child is discharged from the hospital and/or at follow-up visits or clinics. Eligible parents/caregivers may also receive the study brochure or flyer via mail and or email (see recruitment email). The study brochure and flyer includes a QR code to a website that has the information sheet for the study. Research personnel will connect with families at the hospital (e.g., at follow-up clinics or discharge) or via phone (see phone /in-person recruitment script). Parents will be provided information about the study during this contact and will have the opportunity to review the information sheet/consent form and ask questions. Study staff will document this consent process on a form that will be included in the study binder.

Recruitment through sharing of study information and flyer

Potential participants may also reach out to the study staff and request to be screened for the study. Study staff at CCHMC will screen potential participants for eligibility and families who meet criteria will be provided information about the study during this contact and will have the opportunity to review the information sheet/consent form and ask questions (see Road-to-recovery telephone script for potential participants who self refer). Study staff will document this consent process on a form that will be included in the study binder

For all

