If the parent or individual is not interested, they will be thanked for their time and no further contact about the study will be made. If interest in the study is expressed, the parent will be sent a link to the study REDCap site. Parents will also be given the option to meet with study staff via videocall to orient the parent to the REDCap and/or study site and provide technical support. The study REDCap site opens with the study information sheet that provides contact details for study personnel. Participants who choose to participate will indicate consent by clicking a button at the bottom of the REDCap information sheet that reads, “YES, I acknowledge that I have viewed the information sheet and am voluntarily choosing to participate in this study.” Participants who click “YES” will then begin the baseline questionnaires. Participants who choose not to participate will click the “NO, I acknowledge that I have viewed the information sheet and I do not wish to participate in this study,” and they will receive a notification thanking them for their time and they will not be able to access the questionnaires.

After baseline measures have been completed, the predetermined randomization sequence will be used to randomize caregivers into one of the two conditions (R2R-TBI vs. IRC). Stratified randomization will be used to achieve balance in child’s age (< 5 years; ≥ 5 years) and injury severity. The randomization sequence will be based on a design with blocks of four or six chosen randomly within the sequence with equal probability. A pseudorandom number generator in R will be used, and the randomization sequence will be maintained by the statistician. Randomly varying block size reduces the chance that research staff will guess the next group assignment, minimizing unconscious bias. Block randomization with randomly mixed block sizes will then be performed with equal probabilities of assigning a participant to one of the two intervention groups.

4. Study Procedures

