5.1 Statistical and Analytical Plans

Caregiver functioning is examined as the primary and most proximal outcomes of the R2R-TBI intervention. Through targeting caregiver functioning, we expect the R2R-TBI intervention to have downstream effects (through reductions in caregiver depression and distress) on the secondary outcomes of child recovery and family functioning. We further anticipate that the same risk and protective factors that have been shown to moderate child recovery and the efficacy of other family-centered interventions for pediatric TBI, such as household income and baseline family functioning, will moderate the efficacy of the R2R-TBI intervention (e.g., Antonini et al., 2014; Raj et al., 2014b; Wade et al., 2012, 2015). Specifically, we anticipate that the R2R-TBI intervention will be most effective among low-income families and among caregivers with high levels of baseline distress. Our hypotheses are as follows:

Hypothesis 1: Caregivers receiving the R2R-TBI intervention will report lower levels of depression, anxiety, post-traumatic stress, and higher levels of caregiver self-efficacy and mindful self-care at follow-up, compared to caregivers in the IRC condition, after controlling for baseline levels.

The R2R-TBI intervention is designed to promote caregiver psychological well-being and positive parenting in the acute phase post-injury. This hypothesis represents an important test of whether the intervention is successful in improving these areas of functioning that are targets of the intervention. To evaluate this hypothesis, we will examine group difference in caregiver depression (CES-D-10, Radloff, 1977), anxiety (PROMIS Anxiety 4a), post traumatic stress (PC-PTSD-5, Prins et al., 2015), caregiver self-efficacy (CSES, Boothroyd & Evans, 1997), and mindful self-care (MSCS-25; Cook-Cottone, 2015) at one and six-months post-baseline, controlling for baseline scores. Given the challenges in the acute phase post-injury, we expect caregivers in the R2R intervention to report stable functioning while caregivers in the IRC group to report increasing levels of depression and distress at both one and six-month follow-ups.

Hypothesis 2: Caregivers receiving the R2R intervention will report better child and family functioning at follow-up, compared to caregivers in the IRC condition, after controlling for baseline functioning.

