We anticipate that the R2R-TBI intervention will be effective in both ameliorating problems evident at baseline and in preventing emergence of additional problems in family and child functioning at one and six-months post-baseline. To test this hypothesis, we will examine group differences in family functioning (FAD-GF, Epstein, Baldwin, & Bishop, 1983), family burden of injury (FBI, Burgess et al., 1999) and child socioemotional functioning (PedSQL Psychosocial Summary Score, Varni et al., 1999) at one and six-months post-baseline.

Hypothesis 3: We hypothesize that treatment effects will be moderated by household income and level of caregiver distress at baseline.

We expect families with greater social disadvantage (lower income, more stress) will benefit most from the R2R-TBI intervention. This hypothesis is consistent with previous research findings (e.g., Antonini et al., 2014; Raj et al., 2014b; Wade et al., 2012, 2015).

Variable distributions will be examined before carrying out inferential statistical procedures, and transformations will be made in cases where distributions are skewed or fail to meet the assumptions of normality. Non-parametric procedures will be employed in cases where transformations would be inappropriate or where analysis of frequencies is justified. Preliminary work will also involve computation of reliabilities and creation of derived variables that summarize performance on measures that are highly inter-correlated. To evaluate potential attrition bias, caregivers who drop out (i.e., those who access < 3 modules and/or who do not complete baseline or follow-up measures) will be compared to those who remain in follow-up on background characteristics as well as on outcomes measured prior to dropout. Factors related to dropout will be included as covariates in the analysis.

Analytic plan for hypotheses 1 and 2. The primary analysis will consist of a linear mixed-effect models used to examine changes in caregiver, family, and child functioning among participants in the R2R-TBI intervention and IRC groups from baseline to 6-months post-baseline. In addition, the one-month data will be included in a mixed model repeated measures analysis. This model allows for flexible modeling of the pattern of change in outcomes over time and uses all the data for a given participant, even if that participant is not seen at all assessments, allowing us to retain participants with missing assessments.

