Analytic plan for hypothesis 3. Existing literature and findings from our other studies suggest that demographic factors such as household income as well as baseline caregiver functioning impact adaptation to injury, and we hypothesize that these factors will moderate the efficacy of the intervention. Hierarchical multiple regression analyses which include the interaction of group, moderator (household income, baseline functioning), and time in the model will be used to test hypothesis 3. Variable selection using backward elimination will be used to remove non-significant higher- and then lower-order terms. In order to avoid selection bias, bootstrapping will be used on the backward elimination process (Austin, 2008). Post hoc analyses will be used to compare

treatment groups on each outcome at different levels of the moderators at 1 and 6-months post-baseline.

6. Data Management

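### Household income, which the plan treats as prognostic and collects at baseline, should be a fixed covariate in the Hypothesis 1 and 2 models instead of entering only if it is related to dropout; the gain is small

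*Combined protocol and SAP*

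**What the plan says.** The plan gives income a prognostic role in two places. Section 1.1 lists "lower household income" among the risk factors for poorer recovery, together with greater injury severity and younger age. The analytic plan for Hypothesis 3 in section 5.1 states that "demographic factors such as household income as well as baseline caregiver functioning impact adaptation to injury".

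Section 3.3 has every caregiver complete a "demographic survey that includes items related to annual family income". Section 4.1.2 requires complete baseline forms before randomisation, so the variable is available as a true baseline covariate. Section 3.5 stratifies randomisation by child age and injury severity, not by income.

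For Hypotheses 1 and 2, section 5.1 specifies linear mixed models and control for the baseline level of the outcome. Its only other covariate rule is that variables found to be related to dropout are added. Income is a named model term only under Hypothesis 3, as a moderator. The stratification factors are not named as covariates anywhere.

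**The concern.** A baseline variable that predicts outcome reduces residual variance when it is in the model, and here it has already been paid for. Under the plan, whether income is used depends on who drops out and not on the prognostic role that the plan gives it. The set of covariates in the primary model therefore cannot be written down before the follow-up data are seen, and no test or threshold for the dropout comparison is stated.

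The dropout definition adds to the difficulty. It counts caregivers who access fewer than three modules, but the comparison arm has no modules (section 4.1.3.2). The rule thus mixes adherence in one arm with loss to follow-up in both.

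At stake are a little precision, a firmer pre-specified model, and a somewhat more credible missing-at-random assumption for the mixed model.

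**Working it through.** **Inputs from the documents.** "Up to 200 participants will be enrolled in this RCT" (section 3.5), with allocation by "equal probabilities of assigning a participant to one of the two intervention groups", so at most 100 per arm. Assessments are at baseline, one month and six months. The plan gives no power calculation, effect size, SD, dropout rate or income-outcome correlation, so there is no figure of its own to reproduce.

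**Assumptions.** Outcomes are in SD units. The correlation between any two visits is ρ = 0.5 to 0.7. The correlation of income with the outcome is r = 0.1 to 0.3.

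**Step 1: constant association.** If income correlates r with the outcome at baseline and at follow-up alike, its partial correlation with follow-up given the baseline score is

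r_p = r(1 − ρ) / √[(1 − r²)(1 − ρ²)],

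and adding income multiplies the standard error (SE) of the group effect by √(1 − r_p²).

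| ρ | r | r_p² | SE factor |
|---|---|---|---|
| 0.5 | 0.1 | 0.0034 | 0.998 |
| 0.5 | 0.3 | 0.0330 | 0.983 |
| 0.6 | 0.2 | 0.0104 | 0.995 |
| 0.7 | 0.1 | 0.0018 | 0.999 |
| 0.7 | 0.3 | 0.0175 | 0.991 |

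The gain is 0.1 to 1.7%. Baseline adjustment has already absorbed most of what income could explain.

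**Step 2: cost of a term.** With 200 analysed, one uninformative term multiplies the SE by √(197/196) = 1.0025, or about 0.25%. One term breaks even at r_p² = 1/197 = 0.005. At r = 0.1 the net effect is therefore nil or very slightly negative; at r = 0.3 it is a gain of about 0.6 to 1.4%.

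**Step 3: association that grows over time.** This uses the generalised least squares variance of the six-month group effect in a three-visit mixed model, with 100 per arm, complete data and ρ = 0.6. In the baseline-controlled form, the SE without income is √[(2/100)(1 − 0.36)] = 0.113. In an unconstrained group-by-time change model it is √[(2/100) × 2(1 − 0.6)] = 0.126. The table gives SE factors after adding income.

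| Income-outcome correlation at the three visits | Baseline-controlled: main effect | Baseline-controlled: income by time | Change model: main effect | Change model: income by time |
|---|---|---|---|---|
| 0.2, 0.2, 0.2 | 0.995 | 0.995 | 1.000 | 1.000 |
| 0.1, 0.2, 0.3 | 0.972 | 0.953 | 1.000 | 0.975 |
| 0.2, 0.3, 0.4 | 0.952 | 0.934 | 1.000 | 0.975 |
| 0.0, 0.2, 0.3 | 0.967 | 0.927 | 1.000 | 0.942 |

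With a growing association, income by time gains about 5 to 7% in the baseline-controlled form. In the change model an income main effect gains nothing, and only the interaction with time can help. Section 5.1 speaks both of controlling for baseline and of examining change, so it does not settle which form applies.

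**Step 4: bias from loss to follow-up.** With complete data there is none. If income drives loss equally in both arms there is also none. Bias needs loss that depends on income differently by arm. For scale, take 22% loss in one arm made up entirely of the poorest 22%. Mean income among those retained then shifts by φ(−0.772)/0.78 = 0.38 SD. With an income effect of 0.3 SD the bias is 0.38 × 0.3 = 0.11 SD, the ceiling for one-arm loss under these assumptions.

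**The case against.** The case for leaving the plan alone has four parts.

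- **The prognostic statements are indirect for the primary outcomes.** Section 1.1 concerns the child's recovery, while Hypothesis 1 concerns caregiver outcomes. The Hypothesis 3 wording is broader, but it introduces moderators. This stands as a reason not to assume a large correlation. It does not remove the plan's own statement.
- **Income is not excluded.** The text is silent, and the dropout rule would often bring income in. In a simulation with 200 participants, about 22% loss, income-related loss in one arm only and a 0.05 test, income was flagged in about 72% of trials at a dropout odds ratio of 2.7 per SD of income and in 91% at 4.5. If loss ran in opposite directions by arm, it was flagged in only about 6%. So the rule covers part of the problem and misses the case with the larger bias.
- **The standard error already allows for chance imbalance.** This is correct. The lack of stratification by income is not a defect in itself.
- **Income is not special.** Child age and injury severity are also called risk factors, are stratified on, and are unnamed as covariates. This is right, and the fix should cover all three.

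A reader might infer that the treatment comparison is biased, or that 200 caregivers could be made to do the work of about 220. The documents support neither. The second reading needs a correlation of 0.3 beyond the baseline score (200/(1 − 0.09) = 220), which a constant association of 0.3 does not produce once baseline is controlled. The first needs income-related loss that differs between arms, about which the documents say nothing.

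**Conclusion.** The point holds as a modest matter of efficiency and pre-specification. The plan calls income prognostic, collects it before randomisation, and then lets observed attrition decide whether the Hypothesis 1 and 2 models use it.

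Under the assumed constant correlations the SE would fall by about 0.1 to 1.7% before the small cost in degrees of freedom. A fall of about 5 to 7% needs an association that grows over time, an income-by-time term and a baseline-controlled model. All these figures rest on assumed correlations, since the documents supply none.

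Any reduction in bias is conditional on income-related loss that differs by arm, and the dropout rule would cover part of it. The complete-data comparison remains valid without the change.

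**What to change.** In section 5.1, state that every Hypothesis 1 and 2 model includes, whatever the dropout comparison shows:

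- the baseline score of the outcome;
- household income as recorded at baseline, in one stated coding, with a missing category so that no caregiver is lost for declining the item;
- the interaction of income with time;
- the two stratification factors, child age and injury severity.

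Specify the baseline value of income explicitly, because the opening sentence of section 3.3 has the listed measures completed at all three assessments. The dropout comparison can stay as a description of attrition, with any covariates it suggests used in a sensitivity analysis.

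The cost is a sentence or two of text and a few degrees of freedom. Three uninformative terms would raise the SE by √(197/194) = 1.008, about 0.8%, which favours a single ordered income score plus a missing indicator over many separate bands. No new data are needed.

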4.1.2 Enrollment/Baseline

Eligible caregivers who provide consent via REDCap will be presented with the baseline survey queue on REDCap. The baseline forms are expected to take about

45 minutes to complete. Once study staff receive complete baseline forms, participants will be randomly assigned to either IRC or R2R-TBI and will be sent a link, password, and instructions on how to access the R2R-TBI application or IRC website.

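### Baseline caregiver distress, which the plan treats as prognostic, is not prespecified as a covariate for the secondary child and family outcomes of Hypothesis 2, so a small, nearly free gain in precision is left to chance

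*Combined protocol and SAP*

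**What the plan says.** The plan treats the caregiver's starting state as prognostic in two places. Section 1.1 reports that "Poor caregiver psychological functioning and family dysfunction have been found to exacerbate child behavior problems following injury". Section 5.1, in the analytic plan for Hypothesis 3, says that household income "as well as baseline caregiver functioning impact adaptation to injury".

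The scores are available in time. Section 3.3 lists the CES-D-10, PROMIS Anxiety 4a and PC-PTSD-5 at baseline, and section 4.1.2 says "Once study staff receive complete baseline forms, participants will be randomly assigned". They are not balanced by design. Section 3.5 states: "Stratified randomization will be used to achieve balance in child’s age (< 5 years; ≥ 5 years) and injury severity".

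For the child and family outcomes, Hypothesis 2 expects "better child and family functioning at follow-up, compared to caregivers in the IRC condition, after controlling for baseline functioning". The text beneath it says "we will examine group differences in family functioning", together with family burden of injury and the PedsQL psychosocial score, at one and six months. What baseline functioning means is not defined. The analytic plan for Hypotheses 1 and 2 names a linear mixed model and lists no covariates. The paragraph before it compares dropouts with completers on background characteristics and earlier outcomes, and adds as covariates whatever proves related to dropout.

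Baseline functioning is named as a model term only in the Hypothesis 3 regressions, as a moderator subject to backward elimination.

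**The concern.** A variable that the sponsor already believes to be prognostic, measured before allocation, is the standard candidate for a prespecified covariate. The caregiver who reports distress also rates family functioning, injury burden and the child's quality of life, so baseline mood could predict later ratings beyond what the outcome's own baseline captures.

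As written, whether caregiver distress enters a Hypothesis 2 model depends on its association with dropout in the trial's own data. That is a different question from whether it predicts the outcome. The dropout definition is also awkward as a gateway. It includes opening fewer than three modules, although under section 4.1.3.2 the comparison arm receives no modules.

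At stake are somewhat wider intervals than necessary for three secondary outcomes, and a covariate set that is settled only after follow-up data are seen.

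**Working it through.** **Inputs from the documents.** Section 3.5: "Up to 200 participants will be enrolled in this RCT", with "equal probabilities of assigning a participant to one of the two intervention groups", so about 100 per arm at most. The documents give no significance level, power, effect size, standard deviation, dropout rate or correlation, so there is no stated figure to reproduce.

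**Assumptions.**
- r is the partial correlation of baseline distress with the 6-month outcome, given the outcome's own baseline: 0.1 to 0.35.
- rho is the correlation of the outcome with its own baseline: 0.6.
- The test is two-sided at 5%, with all 200 caregivers analysed.

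**Step 1: precision.** Adding the covariate multiplies the variance of the arm difference by 1 − r², and the standard error by √(1 − r²). The equivalent sample size without it is 200/(1 − r²). For an effect that has 80% power with own-baseline adjustment alone, power becomes Φ(2.80/√(1 − r²) − 1.96).

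| r | 1 − r² | SE factor | SE reduction | Equivalent N | Power |
|---|---|---|---|---|---|
| 0.10 | 0.9900 | 0.995 | 0.5% | 202 | 80.4% |
| 0.20 | 0.9600 | 0.980 | 2.0% | 208 | 81.6% |
| 0.30 | 0.9100 | 0.954 | 4.6% | 220 | 83.6% |
| 0.35 | 0.8775 | 0.937 | 6.3% | 228 | 84.9% |

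The percentage reduction does not depend on N. With 160 caregivers the equivalent sizes run from 160/0.99 = 162 to 160/0.8775 = 182.

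**Step 2: chance imbalance.** At 100 per arm, the arm difference in a standardised baseline score has standard deviation √(2/100) = 0.141 and a 95% range of ±1.96 × 0.141 = ±0.28. The standard error of the own-baseline-adjusted arm difference is √(1 − 0.36) × 0.141 = 0.8 × 0.141 = 0.113 outcome SD. Suppose the part of distress not explained by the outcome's own baseline is imbalanced at that 95% limit. The shift is then r × 0.8 × 0.28: 0.02 outcome SD at r = 0.1, 0.07 at r = 0.3 and 0.08 at r = 0.35. The effect detectable with 80% power is 2.80 × 0.113 = 0.32 SD.

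**Step 3: is the test still valid without the covariate?** In 20,000 simulated trials per value of r (N = 200, rho = 0.6), type I error with own-baseline adjustment alone was 0.048 at r = 0.1, 0.052 at r = 0.3 and 0.048 at r = 0.5. Power without and with the covariate was 0.792 and 0.793 at r = 0.1, and 0.794 and 0.830 at r = 0.3.

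**Step 4: form of the model.** Section 5.1 leaves open whether baseline is a covariate or one of the repeated responses. If it is a response, a distress term with the same coefficient at every visit adds the same amount at baseline and at follow-up and cancels from the change. The term then needs its own coefficient at each visit. The factor in Step 1 is exact for own-baseline adjustment with complete data and only approximate for a mixed model with missing visits.

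**The case against.** The strongest reply is that nothing is invalid and the gain may be negligible. That stands. At r = 0.1 power hardly moves, and the documents give no partial correlation. The same-rater argument also cuts both ways: if mood colours later ratings, it colours the baseline ratings too, and adjusting for the outcome's own baseline already removes part of it. The outcomes are secondary.

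Three stronger readings are tempting, and the documents do not support them.
- A reader might infer that the Hypothesis 2 models adjust for the outcome's own baseline and nothing else. That is the natural reading of an undefined term, but section 5.1 does not say it, and dropout-related factors, which could include baseline caregiver scores, are to be added.
- A reader might infer that chance imbalance in distress biases the result. It does not: the shift in Step 2 is chance variation that the standard error already reflects, and an imbalance beyond the limit used there occurs in about 5% of randomisations.
- A reader might see a contradiction in Hypothesis 3 containing a term that Hypothesis 2 lacks. Hypothesis 3 asks about interaction, so its moderator belongs in that model; this does not oblige the main-effect model to carry it.

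It is also fair to say that household income is named in the same sentence as caregiver functioning, and that the stratification factors are likewise missing from the stated model. This widens the request to specify covariates but does not answer the point about distress. Finally, complete covariate data are likely but not certain: section 4.1.2 randomises after complete baseline forms, while the dropout definition in section 5.1 allows for caregivers who did not complete baseline measures.

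**Conclusion.** The point holds as a modest matter of efficiency and specification. The plan regards baseline caregiver functioning as prognostic, collects it before allocation, does not stratify on it, and does not guarantee it a place in the Hypothesis 2 models. Under the assumed partial correlation of 0.1 to 0.35, prespecifying it is worth about 0.5% to 6% of the standard error, or roughly 2 to 28 caregivers on 200. The size rests on that assumption and on enrolment reaching its ceiling. The case for acting does not need the upper end, because the change is valid at any correlation and takes the choice of this covariate out of the data-driven screen.

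**What to change.** In the analytic plan for Hypotheses 1 and 2, state that each Hypothesis 2 model adjusts for the outcome's own baseline and for one pre-named baseline caregiver distress score as a fixed covariate, whether or not that score relates to dropout. The CES-D-10 total is one candidate; the sponsor may prefer another scale already collected, provided it is named in advance. This also defines baseline functioning for Hypothesis 2. If baseline is modelled as a response, add the score's interaction with visit. Use the same score as the caregiver-distress term in the Hypothesis 3 models. The same sentence is a good place to say whether household income and the stratification factors are included.

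The cost is a sentence or two of text and no new data. It takes one extra coefficient when baseline is a covariate, or one per modelled visit when baseline is a response: two for baseline and six months, three if the one-month visit is included.
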